5.7.1.4. Sensitivity Analyses and Additional Analyses

Several sensitivity analyses will be conducted to evaluate the robustness of the primary analysis method and the impact of missing CV event data due to early study discontinuation. An additional analysis for the primary endpoint using CV events per investigator assessment instead of CEC will also be conducted using the primary analysis approach (Section 5.7.1.4.2).

5.7.1.4.1. Win Ratio Analysis

The composite outcome endpoint of all-cause mortality and recurrent CV events will be analyzed using a win ratio method [Dong 2018], stratified by baseline NT-proBNP group. The overall population analysis will also be stratified by baseline tafamidis use. The win ratio statistic is

calculated from the ranking of each possible vutrisiran-placebo pair based on survival time and the frequency (count) of CV events in a hierarchical order. In this analysis, all-cause mortality is given higher importance than the frequency of CV events. Vital status collected after study discontinuation will be used in the ranking procedure. The point estimate of the win ratio as well as 95% CI and p-value will be generated. Details of this method are provided in Appendix 9.2.

5.7.1.4.2. Analyses Based on Alternative Definitions of the Composite Outcome

Three separate analyses of the composite outcome of all-cause mortality and recurrent CV events will be performed based on alternative definitions of all-cause mortality or CV events as outlined in Table 7 below. The same model from the primary analysis will be applied.

Table 7: Alternative Definitions of one Component of the Composite Outcome for Three Separate Analyses

Component to be redefined	Alternative Definition of Component
All-cause mortality	Heart transplant and left-ventricular assist device (LVAD) placement are not included in all-cause mortality. Patients will be censored at the date of such procedure or at the censoring date described in Section 4.5, whichever is earlier.
CV events	In addition to the CV events defined in the primary analysis, CCI [REDACTED] CCI [REDACTED]
CV events	Using CV events per investigator assessment instead of CEC

CCI [REDACTED]
[REDACTED]
[REDACTED]

5.7.1.4.4. Analysis Based on Imputing CV Events after Study Discontinuation

A two-stage multiple imputation (MI) process that follows the procedure for monotone missing data [Rubin 1987] will be used to assess the sensitivity of the primary analysis for any missing CV events due to early study discontinuation. Missing CV events will not be imputed after death. The imputation will be done for up to the last survival follow-up date in the DB period as defined in Table 2 for patients who discontinued the study. For each imputed dataset, the same LWYY model as the primary analysis will be applied. The results will be combined using Rubin's rule [Rubin 1987]. Details of the two-stage MI approach are provided in Appendix 9.3.

CCI [REDACTED]
[REDACTED]
[REDACTED]

5.7.1.4.6. Summary of Sensitivity analyses

The rationale and difference in handling ICEs comparing with the primary analysis approach are summarized for each sensitivity analysis in the following table.

Sensitivity analysis	Differences from the primary analysis in assumptions or handling approach for ICEs and Rationales
Win ratio analysis (Section 5.7.1.4.1)	CCI [REDACTED]
HT or LVAD placements are not treated as death (Section 5.7.1.4.2)	In the primary analysis, Composite variable strategy is used for intercurrent event of HT or LVAD placement, which treats them as death. In this sensitivity analysis, Hypothetical strategy is used to censor patients at the time of HT/LVAD placement.
CCI [REDACTED]	CCI [REDACTED]
CCI [REDACTED]	CCI [REDACTED]
Analysis based on imputing CV Events after study discontinuation (Section 5.7.1.4.4)	In the primary analysis, patients who discontinued study not due to death, HT or LVAD placement are censored at the last event follow up date during the DB period (defined in Table 3). In this sensitivity analysis, CV events are imputed after the study discontinuation to assess the impact of missing CV event due to early study discontinuation.
CCI [REDACTED]	CCI [REDACTED]

5.7.2. Secondary Endpoints

This section defines the estimands and analysis methods for the secondary endpoints. In the estimands, the first two elements “Target Patient Population” and “Treatment Condition” are the same as the primary endpoints and will not be repeated in the descriptions.

5.7.2.1. 6-MWT and KCCQ-OS

The scoring algorithm for the KCCQ-OS is included in Appendix 9.8 .

5.7.2.1.1. Definition of Estimand

For the objective of evaluating the efficacy of vutrisiran compared with placebo on 6-MWT and KCCQ-OS after 30 months of treatment, the estimands are defined as follows:

- **Endpoint:** Change from baseline in 6-MWT/KCCQ-OS at Month 30 (Week 132)
- **Population-level summary:** The Least Square (LS) mean difference in the change from baseline in 6-MWT/KCCQ-OS at Month 30 between the vutrisiran and placebo arms.
- **Intercurrent events (ICE) strategies:** Intercurrent events include treatment discontinuation, death, progression of ATTR amyloidosis, initiation of alternative therapies, and COVID-19 infection. They require different handling strategies, described in [Table 8](#) below.

Table 8: Intercurrent Event Strategies for the Primary Analysis of 6-MWT and KCCQ-OS

Intercurrent Event	Strategy with Rationale
Treatment discontinuation	Treatment policy strategy: Intercurrent event is ignored; 6-MWT/KCCQ-OS assessments obtained after treatment discontinuation will be included in analysis.
Death (including heart transplant and LVAD placement)	CCI

Intercurrent Event	Strategy with Rationale
Unable to walk due to progression of ATTR amyloidosis (applicable to 6-MWT only)	Composite variable strategy: The missing 6-MWT change will be imputed using the same approach as death.
Initiation of alternative therapies: 
• Tafamidis drop-in in the vutrisiran monotherapy subgroup• CCI [REDACTED]• Prohibited medications including inotersen, commercial patisiran and vutrisiran	Treatment policy strategy: Intercurrent event is ignored; 6-MWT/KCCQ-OS assessments obtained after the initiation of alternative therapies will be included in analysis.
COVID-19 infection	Treatment policy strategy: Intercurrent event is ignored; 6-MWT/KCCQ-OS assessments after COVID-19 infections will be included in analysis.

5.7.2.1.2. Primary Analysis

CCI

CCI

CCI

5.7.2.1.3. Sensitivity Analysis

An alternative estimand is to estimate the changes from baseline and treatment effects at scheduled visits for patients who were alive at the visits. The analysis will be based on the same MMRM model as the primary analysis with different ICE handling strategy for death. Missing data due to death will not be imputed with worst outcome and will be assumed as MAR. For 6-MWT, missing due to unable to walk due to progression of ATTR amyloidosis will still be imputed with worst outcome, the same as in the primary analysis.

A sensitivity analysis using PMM will also be performed to assess the robustness of the primary MMRM results to the possible violation of the MAR missingness assumption. The PMM accommodates situations where the missingness mechanism may be MNAR. Unlike the primary analysis, this sensitivity analysis imputes the missing data based on different missing patterns. More details on the PMM are provided in Appendix 9.4.

5.7.2.2. All-Cause Mortality

5.7.2.2.1. Definition of Estimand

For the objective of evaluating the efficacy of vutrisiran compared with placebo on all-cause mortality, the estimand is defined as follows:

- **Endpoint:** time from the first dose to death from any cause (including heart transplantation and LVAD placement)
- **CCI**
- **Intercurrent events (ICE) strategies:** The ICE handling strategies are described in Table 9 below.

[figure not shown]
Table 9: Intercurrent Event Strategies for All-cause Mortality in Different Analyses

Intercurrent Event	Secondary endpoint all-cause mortality: primary analysis (over 42 months)	Secondary endpoint all-cause mortality: additional analysis including data during the study	Component analysis of all-cause mortality for the primary endpoint (over 36 months)
Study discontinuation	Treatment policy strategy		
Cross-over to vutrisiran in the OLE period (placebo patients)	Hypothetical strategy: for both vutrisiran and placebo arms, all vital status data during the DB period and within	Treatment policy strategy: ICE ignored; all data included in analysis	Hypothetical strategy: data censored at the first OLE dose date

Intercurrent Event	Secondary endpoint all-cause mortality: primary analysis (over 42 months)	Secondary endpoint all-cause mortality: additional analysis including data during the study	Component analysis of all-cause mortality for the primary endpoint (over 36 months)
	the first 6 months of OLE period will be included in the analysis. Data after 6 months of the first dose in OLE will be censored.		
Initiation of alternative therapies (other than cross-over)	Treatment policy strategy		
Deaths related to COVID-19	Treatment policy strategy		
Heart transplantation and LVAD placement	Composite variable strategy: treated as CV-related death.		

5.7.2.2.2. Primary Analysis

CCI

5.7.2.2.3. Additional Analysis

CCI

CCI

Month 30 and Month 33 survival rates will be analyzed using the Cochran-Mantel-Haenszel (CMH) method, stratified by baseline NT-proBNP group and baseline tafamidis use (for the overall population only). Common risk difference with corresponding CIs and p-values will be reported. Since not all patients will have 36 months of survival follow-up by the time of primary analysis data cut, Month 36 survival rate will not be analyzed.

Time to CV-related death (including deaths with CV and indeterminate causes, heart transplants, and LVAD placement) will be analyzed.

The analysis of all-cause mortality will also be conducted including data collected during the study (including data after 6 months of the first dose in OLE). The overall HR and p value will be estimated using similar methods as for the primary analysis.

5.7.2.3. NYHA Class

5.7.2.3.1. Definition of Estimand

For the objective of evaluating the efficacy of vutrisiran compared with placebo on NYHA Class change from baseline after 30 months of treatment, the estimand is defined as follows:

- **Endpoint:** Proportion of patients with stable or improved NYHA class at Month 30 (Week 132)
- **Population-level summary:** Difference in proportion of patients with stable or improved NYHA class at Month 30 comparing vutrisiran with placebo .
- **Intercurrent events (ICE) strategies:** For ICEs of treatment discontinuation, initiation of alternative therapies and COVID-19 infection, the treatment policy strategy will be used, i.e., NYHA class collected after these ICEs will be included in analysis. For ICEs of death (including heart transplant and LVAD placement), the composite variable strategy will be used, i.e., the NYHA class after death will be imputed as NYHA class IV.

5.7.2.3.2. Primary Analysis

The change from baseline in NYHA class at Month 30 will be dichotomized into two categories: stable/improved vs. worsened. Missing data not due to death will be imputed using multiple imputation assuming MAR, with details provided in Appendix 9.5. Each dataset will be analyzed using CMH method stratified by baseline NT-proBNP. The overall population analysis will also be stratified by baseline tafamidis use. The common risk difference and standard error from all datasets will be combined by Rubin's rule to get the estimates of treatment difference, 95% CI and p value for the proportion of being stable or improved.

Descriptive summary will be provided, including the number of percentage of patients with improving, stable, and worsening in NYHA class at each visit, and the shift from baseline to Month 30 in NYHA class.

5.7.2.3.3. Sensitivity Analysis

[figure not shown]
[figure not shown]
[figure not shown]
[figure not shown]
[figure not shown]
[figure not shown]
[figure not shown]
[figure not shown]
[figure not shown]
The change from baseline in NYHA class will be treated as a continuous variable and analyzed using MMRM model. The model includes treatment, baseline NYHA class, baseline NT-proBNP, visit, and treatment-by-visit interaction as fixed effect terms. The overall population analysis will also include baseline tafamidis use and treatment-by-baseline tafamidis use interaction as fixed effect terms. The ICEs handling is the same as that for the primary analysis approach.

5.7.3. Exploratory Endpoints

[figure not shown]
CCI

[figure not shown]
CCI

CCI

CCI

5.7.4. Evaluation of Subgroups

All analysis and summary results are presented by baseline tafamidis use subgroups, with vutrisiran monotherapy subgroup defined as an analysis population and background tafamidis defined as a key subgroup. Additionally, subgroup analyses will be conducted to assess the consistency of treatment effect within various subgroups defined by baseline characteristics as listed in the following table.

Subgroup	Overall population	Vutrisiran Monotherapy subgroup
Baseline tafamidis use (yes; no)	Yes	N/A
Age group (<75; ≥75)	Yes	Yes
ATTR disease type (hATTR; wtATTR)	Yes	Yes
NYHA class (I/II; III)	Yes	Yes
Baseline NT-proBNP (≤2000; >2000 ng/L)	Yes	Yes

Subgroup analyses will be performed for the composite endpoint of all-cause mortality and recurrent CV events, 6-MWT, KCCQ-OS, all-cause mortality, NYHA class, and recurrent CV events in both the overall population and vutrisiran monotherapy subgroup. The analyses will be conducted based on the subgroup data only.

- Composite endpoint of all-cause mortality and recurrent CV events:

Composite endpoint of all-cause mortality and recurrent CV events will be analyzed by LWYY model including treatment and baseline NT-proBNP as covariate. For subgroup analysis in the overall population, the model will also be stratified by baseline tafamidis use.

- Change from baseline in 6-MWT and KCCQ-OS:

Change from baseline in 6-MWT and KCCQ-OS will be analyzed by MMRM model with baseline value as a covariate, and treatment, visit, treatment-by-visit interaction as fixed effects. For subgroup analyses in the overall population, the model will also include baseline tafamidis use as a fixed factor.

- CCI [REDACTED]

- Change from baseline in NYHA class:

The binary outcome (stable or improved vs. worsened in NYHA Class at Month 30) will be analyzed by a CMH method stratified by baseline NT-proBNP. For subgroup analysis in the overall population, the model will also be stratified by baseline tafamidis use.

- Recurrent CV events:

The frequency of CV events will be analyzed by Poisson regression including treatment and baseline NT-proBNP as covariates. For subgroup analysis in the overall population, the model will also include baseline tafamidis use as a covariate.

Forest plots will be generated to illustrate the estimated treatment effect along with 95% CI within each subgroup.

5.7.5. Additional Analyses

An alternative estimand is to assess vutrisiran compared to placebo in the vutrisiran monotherapy subgroup without concomitant use of tafamidis.

- For the composite outcome endpoint, events collected beyond 9 months of tafamidis drop-in will be censored. The same LWYY model as for the primary analysis will be applied.
- For 6-MWT and KCCQ-OS, assessments after tafamidis drop-in will be excluded from the MMRM analysis. Missing data due to death and unable to walk due to progression of ATTR amyloidosis (for 6-MWT only) will not be imputed.

For continuous efficacy endpoints, descriptive statistics will be provided for actual value and change from baseline by visit; descriptive statistics for percentage change from baseline by visit may also be provided, as appropriate.

5.8. Pharmacodynamic Analyses

The PD parameters for this study include serum TTR and vitamin A. For all post-baseline TTR data, only post-baseline TTR assessments collected within 84 days (inclusive) after last dose of

study drug will be summarized. Assessments more than 84 days after last dose of vutrisiran will be presented in listings and individual patients plots only. If a patient who received placebo for the first dose but received any amount of vutrisiran due to dispense errors, the patient will still be grouped as placebo but the data after receiving vutrisiran will be censored.

Summary tables will be provided for observed values, changes, and percentage changes from baseline for each scheduled time point by treatment arm for TTR and vitamin A.

The following parameters, derived using all available serum samples for measurement of TTR and vitamin A levels within the specified windows (including unscheduled), will be summarized using descriptive statistics:

- Maximum percentage reduction in serum TTR and vitamin A over the DB period
- Mean percentage reduction in serum TTR and vitamin A over the DB period
- Mean percentage reduction in serum TTR (trough) during steady state from Month 6 to 30

Subgroup analysis for maximum, mean percentage reduction in serum TTR and mean percentage reduction in serum TTR (trough) during steady state described above will be provided for:

- Age (<75; \geq 75)
- Sex (male; female)
- Race (white; black; all other)
- ATTR disease type (hATTR; wtATTR)
- baseline tafamidis use (yes; no)
- NYHA Class (I/II; III)
- Body weight (<65 kg; \geq 65 kg)
- ADA status (positive; negative)

All PD data will be displayed in data listings.

5.9. Pharmacokinetic Analyses

5.9.1. Study Variables

For vutrisiran, plasma concentrations of vutrisiran will be summarized. Concentration values that are below the lower limit of quantification will be set to zero for analysis.

- Day 1, Week 36, Week 72 (Month 18), Week 132 (Month 30): Predose levels and observed concentration 4-hour postdose (C_p [4 hr]) for vutrisiran

5.9.2. Statistical Methods

Descriptive statistics for plasma concentration will include the number of patients, mean, SD, coefficient of variation, geometric mean, geometric mean coefficient of variation, median, minimum, and maximum. Descriptive statistics and graphical displays of the plasma concentrations of vutrisiran will be presented by nominal sampling day (or week).

Population PK and exposure-response modeling may be performed and will be reported separately, as applicable.

5.10. Anti-Drug Antibody Analyses

The number and percentage of patients with confirmed positive anti-drug antibody (ADA) assay results at any time during the DB Period, as well as treatment-emergent ADA during the DB Period will be summarized. Treatment-emergent ADA consist of treatment-induced ADA and treatment-boosted ADA, as defined below:

- Treatment-induced ADA: Confirmed positive ADA developed de novo after drug administration in patients without preexisting (baseline) confirmed positive ADA
- Treatment-boosted ADA: Confirmed positive ADA after drug administration with ADA titer $>4x$ baseline ADA titer in patients with preexisting (baseline) confirmed positive ADA

The ADA titer results for patients with confirmed positive ADA and treatment-emergent ADA results will also be summarized using descriptive statistics.

For patients with confirmed positive ADA results, spaghetti plots for the serum TTR (ELISA) over time and the plasma concentration of vutrisiran over time will be presented and compared with those with negative ADA results. Effect of positive ADA on efficacy and safety may also be explored.

ADA data and patients with confirmed positive ADA results will be presented in data listings.

5.11. Safety Analyses

For AEs, CMs, procedures, laboratory parameters, vital signs and body weight, and ECG, summaries will be based on data from the date of first dose of study drug through the first dose in the OLE period for patients who entered OLE, or through 84 days after the last dose of study drug for patients who discontinued or completed DB treatment.

For by-visit summaries of safety parameters, only scheduled visits and central laboratory data will be used. For derivation of worst postbaseline values and abnormalities, all available assessments (i.e., scheduled and unscheduled) will be used. For the selected laboratory parameters (such as LFTs), two sets of deviations will be used to determine the worst postbaseline values. One set will be solely using central laboratory data and the other set will make use of both central and local laboratory data.

No inferential safety analysis is planned.

5.11.1. Adverse Events

AEs will be classified by the MedDRA coding system (version 23.0 or later) and displayed in tables and data listings using SOC and PT, unless otherwise specified.

Analyses of AEs will be performed for those events that are considered treatment-emergent, defined as any AE occurring or worsening on or after the first dose of study drug and through the first dose in the OLE period for patients who entered OLE, or the earlier of (84 days after the last dose of study drug, early study discontinuation) for patients who discontinued DB treatment, or

any study drug-related AE. Events with a fully or partially missing onset date will be imputed according to the imputation rule defined in Appendix 9.7 before determining treatment-emergent or not.

Unless otherwise specified, AEs will be summarized by the numbers and percentages of patients reporting a given AE, as well as number of AEs and event rates per 100 patient-years.

An overall table of TEAEs will include:

- any AE
- any AE related to study drug
- any serious adverse event (SAE)
- any SAE related to study drug
- any severe AE
- any severe AE related to study drug
- any AE leading to treatment discontinuation
- any drug-related AE leading to treatment discontinuation
- any AE leading to study drug interruption
- any treatment-related AE leading to study drug interruption
- any AE leading to study discontinuation
- any drug-related AE leading to study discontinuation
- any AE leading to death including those not treatment emergent but deaths occurred after the end of study visit are not included.

Tabulations by SOC and PT will be produced for the following:

- AEs
- Treatment-related AEs
- Severe AEs
- SAEs
- AEs leading to treatment discontinuation
- AEs leading to treatment interruption
- AE leading to study discontinuation
- AEs over time

Tabulations by SOC and PT will be produced for AEs with a higher frequency ($\geq 5\%$ or $\geq 10\%$) in either treatment group.

Tabulations by PT will be produced for the following:

- AEs

- Treatment-related AEs
- SAEs

AEs and AEs related to treatment will also be summarized by severity. A patient contributes only once to the count for a given AE (overall, by SOC, by preferred term). Patients who report multiple occurrences of the same AE (preferred term) will be classified according to the most severe occurrence or the most related occurrence, respectively. An AE with missing severity will be assumed to be severe. An AE with missing study drug relatedness will be assumed to be related. For number of AEs and event rates per 100 patient-years, multiple occurrences of the same AE in a patient will be counted multiple times for that patient.

Adverse events mapping to the Standardized MedDRA query (SMQ) Drug Related Hepatic Disorder will be summarized by SOC and PT. Other SMQs or AE groupings may be evaluated.

Injection site reaction (ISR) events will be summarized. The number and percentage of patients reporting at least one ISR, the number and percentage of patients reporting at least one severe or serious ISR, and the numbers and percentages of patients with different ISR symptoms will be summarized, together with number of events and event rates per 100 patient-years.

AE and SAE summary tables (by SOC and PT) will be separately generated for each of the subgroups below:

- Age group [<75 ; ≥ 75 at randomization]
- ATTR disease type [hATTR; wtATTR]
- NYHA Class [I/II; III]
- Sex (Male; Female)
- Race (White; Black; All other)
- Region (US; Europe; Rest of world)

All AEs will be presented in patient data listings. Listings of all deaths, SAEs, AEs leading to treatment discontinuation or study withdrawal, and AEs mapping to the SMQs as described above will be listed. A listing of ISRs will be presented.

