6. OTHER STATISTICAL ANALYSES

6.1. During Vutrisiran Treatment Period

The long-term safety of vutrisiran will be characterized by the analysis of All Vutrisiran treated Set for the vutrisiran treatment period (Section 4.1). The analysis will include all data on or after the first dose of vutrisiran during either the DB or OLE period:

- For patients who receive vutrisiran in the DB period, data from the DB and OLE periods will be integrated.
- For patients who receive placebo in the DB period and receive at least one dose of vutrisiran in the OLE period, only data after the first dose of vutrisiran in the OLE will be included.

Where applicable, baseline will be defined as described in Section 4.3. Summaries will be presented by placebo/vutrisiran, vutrisiran/vutrisiran, and total for the All Vutrisiran treated Set.

Duration of drug exposure will be defined as last vutrisiran dose date – first vutrisiran dose date + 1, with last vutrisiran date defined as the earliest of the following dates:

- Last vutrisiran dose date + treatment-specific window (83 days if last vutrisiran dose received is 25 mg q3M; CCI [REDACTED])
- Analysis cutoff date
- End of study date

AE and ISR summaries described in Section 5.11.1 will be provided for vutrisiran-emergent adverse events, defined as treatment-emergent adverse events occurring on or after the first dose of vutrisiran treatment through a treatment-specific window following the last dose of vutrisiran (83 days if last vutrisiran dose received is 25 mg q3M; CCI [REDACTED])

[REDACTED] Potentially clinically significant postbaseline abnormalities and shift from baseline to the worst postbaseline status for laboratory, vital signs, and ECG parameters, ADA, concomitant medications, and overall study drug exposure, during the vutrisiran treatment period will be summarized.

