 - Otherwise, impute the missing day of the start date as 1.
 - If the above leads to a date after the end date, impute the missing day of the start date using the day of the end date.

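### The double-blind safety window runs through the first open-label dose, so adverse events that start later that day can be counted under placebo

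*SAP*

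**What the plan says.** - **Window end for AEs.** SAP 5.11.1 takes events "on or after the first dose of study drug and through the first dose in the OLE period for patients who entered OLE". A second limb adds "any study drug-related AE" and gives no end date of its own.
- **Window end for all double-blind safety summaries.** SAP 5.11 sets the same bound for AEs, concomitant medications, procedures, laboratory values, vital signs, weight and ECG: "from the date of first dose of study drug through the first dose in the OLE period for patients who entered OLE".
- **Window start for vutrisiran.** SAP 6.1 defines vutrisiran-emergent AEs as "treatment-emergent adverse events occurring on or after the first dose of vutrisiran treatment through a treatment-specific window". For former placebo patients it adds that "only data after the first dose of vutrisiran in the OLE will be included".
- **Definition of double-blind exposure.** SAP 2.1 and protocol 3.1 end it before the first open-label treatment. SAP 5.5 calls the OLE Day 1 dose date the start of the OLE.
- **Handling of vutrisiran given to placebo patients.** SAP 3 moves a placebo patient who receives any vutrisiran in the DB period to the vutrisiran arm for safety. SAP 5.8 censors PD data after such a dose.
- **Partial dates.** SAP 9.7 sets a partial AE start date to the first dose date when month and year agree with that date. If only the day is missing and they do not agree: "Otherwise, impute the missing day of the start date as 1". If day and month are both missing and the year differs, January 1 is used. No rule refers to the first OLE dose.

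**The concern.** Under protocol 3.1 every patient who enters the OLE receives vutrisiran on OLE Day 1. For a former placebo patient this is the first exposure to the drug. The double-blind window is worded to include that dose, and no rule assigns what follows on the same day to vutrisiran alone.

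Same-day reactions are likely to be seen. Protocol 5.2.2 places the first OLE dose in the clinic, and protocol Table 4 schedules PK samples 3 and 6 hours afterwards. They are also reported with knowledge of the treatment, since OLE dosing is open-label.

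Protocol 1.7 names injection-site reactions (ISRs) as an important potential risk, and SAP 5.11.1 reports the percentage of patients with at least one. The double-blind comparison is this trial's placebo-controlled estimate of that risk. If the placebo count is small, a few reactions to vutrisiran placed in that column would visibly change it.

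**Working it through.** The plan states no figure for this point, so there is none to reproduce. The check compares the windows and then sizes the effect under stated assumptions.

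**1. The windows at the boundary.** The double-blind window closes with the first OLE dose (5.11, 5.11.1). The vutrisiran-emergent window opens on or after that dose (6.1). On a calendar-date reading both contain OLE Day 1. On a dose-time reading the first window ends at the injection. The SAP does not say which applies. Its laboratory and vital-sign baselines (4.3) are cut at date and time of dose; the AE window is not.

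**2. Which events are affected.**
- AEs that start on OLE Day 1 after the injection. Those that start on a later day fall outside the dated window.
- AEs in the crossover month with a missing onset day. Setting the day to 1 places them before the OLE dose unless dosing was on the 1st. They then count as placebo and leave the vutrisiran-emergent table.
- Drug-related AEs of any later date, but only if that limb of 5.11.1 is read without the limit in 5.11 and the restriction of SAP Table 1 to double-blind data.

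**3. Size in the placebo column.** Planned size is 600, randomized 1:1, so about 300 on placebo. The documents give neither the OLE entry share (e) nor the same-day reaction rate (r). Assumed: e = 75-90%, r = 1-5%.
- Added patients = 300 × e × r
- Low: 300 × 0.75 × 0.01 = 2.25
- High: 300 × 0.90 × 0.05 = 13.5

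That is about 2 to 14 patients, or 0.75 to 4.5 percentage points of the arm. These are maxima, because a patient with an earlier event is already counted.

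**4. The vutrisiran arm gains an injection too.** The double-blind period holds 12 injections if OLE Day 1 is at Week 144 (144/12) and 13 if at Week 156 (156/12). Assume a true double-blind placebo ISR incidence of 2% and independent reactions at r per vutrisiran injection:
- Low: 1 − 0.99^12 = 11% in the vutrisiran arm
- High: 1 − 0.95^13 = 49%

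Adding OLE Day 1 turns an incidence p into p + (1 − p) × e × r. The difference between arms therefore shrinks by e × r × (p_vutrisiran − p_placebo).
- Low: 0.75 × 1% × (11% − 2%) = 0.07 points
- High: 0.90 × 5% × (49% − 2%) = 2.1 points, against a true difference of 47 points

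The ratio moves more.
- Low: 11/2 = 5.5 becomes (11 + 0.89 × 0.75)/(2 + 0.98 × 0.75) = 11.67/2.74 = 4.3
- High: 49/2 = 24.5 becomes (49 + 0.51 × 4.5)/(2 + 0.98 × 4.5) = 51.3/6.4 = 8.0

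For events per 100 patient-years, both arms gain e × r events per patient. With equal entry and reaction rates the difference is essentially unchanged.

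**5. Follow-up lost by closing the window before the dose.** About 1 day in 1,009 (144 × 7 + 1) to 1,093 (156 × 7 + 1), that is 0.09-0.10%.

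**The case against.** The strongest reply is that the wording already works. SAP 5.11 starts the window at a date but ends it at a dose, so read literally it closes at the injection. SAP 2.1 and Table 1 point the same way. Table shells and specifications are separate documents (SAP 1) and may settle the question. There is also a sound reason for an inclusive bound: the Month 36 and OLE Day 1 assessments can fall on one day (protocol Table 2, footnote a), and their predose values belong to the double-blind period. All of this stands. It shows that the intent is probably right and that the text does not secure it.

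The consequences are also limited. No inferential safety analysis is planned. Fully dated OLE Day 1 events appear under 6.1 as well, and AEs and ISRs are listed by patient. A missing onset day for an ISR given in the clinic is unlikely, since onset time and date are recorded and each ISR has its own form (protocol 6.5.6.2).

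A reader might infer that the rule understates the drug's risk by the full 0.75 to 4.5 points added to placebo. The documents do not support that. Vutrisiran-arm patients entering the OLE are injected on the same day and their reactions enter their own column. A shift of that size would require nearly all their OLE Day 1 reactors to have reacted before, which nothing in the documents states. If more of that arm entered the OLE, the difference in event rates could even widen. Nor does the dated window capture every reaction to the first vutrisiran injection; it captures those that start that day.

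**Conclusion.** The point holds in limited form. As written, SAP 5.11 and 5.11.1 allow an AE that follows a placebo patient's first vutrisiran injection on OLE Day 1 to be tabulated as a placebo treatment-emergent event and again as vutrisiran-emergent. That conflicts with the SAP's own end of double-blind exposure and with its handling of placebo patients given vutrisiran elsewhere.

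The placebo count is inflated by at most about 2 to 14 patients under the assumed entry and reaction rates. The ratio between arms is pulled toward 1 where vutrisiran's rate is higher. The absolute difference may change little: about 0.1 to 2 points in patient incidence under independence, and essentially nothing in event rates if entry and reaction rates are equal. All these figures depend on a calendar-date reading and on rates that the documents do not give. Because safety is descriptive and the dated events also appear under 6.1, this should be corrected but does not threaten the trial's conclusions.

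**What to change.** 1. In 5.11 and 5.11.1, end the double-blind window immediately before the date and time of the first OLE dose, using the AE onset time that protocol 6.5.6.2 already requires.
2. Assign OLE Day 1 events of unknown time to the OLE.
3. Keep predose OLE Day 1 and Month 36 assessments in the double-blind period.
4. Limit the drug-related limb of 5.11.1 to onset before the first OLE dose.
5. In 9.7, for former placebo patients, set a partial AE date that is compatible with the first OLE dose to that dose date.

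The cost is a few lines in the SAP and the programs. No new data are needed. If the database is already locked, SAP 1 provides for the change to be documented and justified in the CSR.

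The change introduces an opposite error. Some same-day events of unknown time, and some true placebo events from before crossover with a missing day, will be assigned to vutrisiran. That is slightly conservative for the drug, and the number of events moved by rules 2 and 5 should be reported.
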